VII: Project management and Monitoring

7.1: Project management

[name] supported by [name] will administer the study. [name] (MSC) will oversee Data Management and clinical monitoring supported by the clinical staff at Meddoc. [name] (MSC) and [name] will oversee the statistical analysis. [name] will evaluate the ophthalmological part of the results.

7.2: Publication of the results

The results will be published in an international medical journal. In principle, all the participating centers will be represented in the list of authors. The rules stated in the Vancouver recommendation will be followed.

7.3: Quality assurance demands

The hospital sites will be monitored at regular intervals at site and electronically during the study. It is the duty of the investigator to provide open access to the monitor to all study related records at previously agreed times and locations.

In conducting the trial, the investigator accepts that the Sponsor, the regional Ethics Committee, the regulatory body, and monitor may, at any time, by appointment, conduct an audit of the study site.

In conducting the trial, the Sponsor accepts that the Ethics Committee or the regulatory body may, at any time, by appointment, conduct an audit of the study site, the laboratories conducting any clinical testing or the Good Manufacturing Practice (GMP) manufacturing facilities.

7.4: Start-up and closing visit

The project manager and the clinical monitor will perform the start-up visit. The visit will consist of a site inspection, information, instruction and handing over the needed study materials as e-CRFs. A training program in use of the electronic data catching system InCRF will be given.

The project manager will perform the closing visit within one month after the last patient on the given site has finalized the study. All the trial material including CRFs will be removed from the site, but copies of the CRFs from the included patients will be stored at the site.

7.5: Monitoring procedure

Essential demographic data will be documented both within the patients' hospital record notes as source data and within the trial e-CRFs. This has to be available for inspection by the clinical trial monitor. Source data will also include the date of written consent. The times and dates of any other investigations must also be recorded.

It is the responsibility of the investigator to maintain accurate and up to date records of all clinical trial related activities, which should be legibly entered onto the e-CRFs provided. The e-CRFs should be made available to the monitor on request, and in the event of a formal investigator site audit.

On completion of the study, one copy of the e-CRFs will be retained at the hospital site for the duration stipulated by International Conference on Harmonization Good Clinical Practice (ICH/CGP), which currently is 5 years.

The eCRFs can be accessed online via web-based database InCRF. The contents of eCRFs should be approved by the investigators.

Monitoring at site will be performed at least three times at each participating hospital during the study. Monitoring report will be sent to the project manager latest one week after each site inspection.

7.6: Curriculum vitae

The investigators have to submit an updated CV documenting their expertise in the relevant clinical field. The CV has to be signed and dated by the physician and a copy has to be attached to the protocol if required according to international rules. Another copy must be kept in the Trial Master File and a third copy in the Site File.

7.7: Site file

On behalf of the Sponsor, Meddoc AS will supply the investigators with a Site File. The Site File should contain all relevant documents for the study. The investigator is responsible for keeping the Site File updated and secure that all required documents are present in the Site File. The Site File will be inspected during the monitor visits.

VIII: Data Management

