Bulbicam will be used in the study and the following six tests will be performed at each investigation: “Neurofield 64”, “Ptosis”, “Dynamic Acuity”, “Dynamic Contrast “, “Dark Adoption” and Pupil. The Standard Method will be used initially for measurements of “Neurofield64”, “Visual Field” and “pupil”.

1.6: Design

The study will be performed as a controlled, open, and non-randomized, stratified observational multicenter study. The stratification factors are the pathology of DR and AMD and the degree of disease. Within each of the four strata, healthy matched controls related to gender- and age (1:1) will be included. The degree of DR is defined as follows:

- 1) Mild retinopathy: Mild nonproliferative diabetic retinopathy
- 2) Moderate retinopathy: Moderate nonproliferative diabetic retinopathy

The degree of AMD is defined as follows:

- 1) Early AMD
- 2) Intermediate

For each included patient, a gender- and age-matched HC will be included. All included participants will perform Bulbicam eye-investigation twice at three flowing days with a rest period of at least one hour. Each investigation includes same six Bulbicam tests. The Standard method will only be performed once as the first investigation at day 1 for measurements of “Visual Field” and Pupil”

1.7: Variables

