The patients will be recruited from Oslo University hospital, Ullevål and Helgeland hospital. If necessary, private Ophthalmology clinics in Oslo will be asked for recruitment. All the investigations in the study will be performed by the same Ophthalmologist at the given hospital. The investigator informs the patients about the study, handing and collecting the written informed consent form. In case the patient fulfils the inclusion/exclusion criteria and willing to sign the consent form, the patient is included in the study. No data from possible participants included in the screening phase but not fulfils the inclusion/exclusion criteria will be recorded in the database. The included patient will be asked if he/she know any person with same gender and age; in good health condition without any eye disease which may participate as a control in the study. The potential controls will be contacted by the responsible investigator, obtain information about the study, and expected tasks. Controls willing to sign the consent form is included in the study. In case of lack in controls, requests among the hospital staff will be performed.

3.4: Benefit and risk assessment

BulbiCam is new equipment specially developed for clinical investigation of eye. It will simplify neuro-ophthalmic examinations; increase the quality- and benefit of the examinations; detecting earlier correct diagnoses and increase the knowledge of the disease development under treatment. BCAM do not harm neither to the patients nor to the investigator.

IV: Design

4.1: Study design

The study will be performed as a controlled, open and non-randomized, stratified observational multicenter. The two stratification factors will be ophthalmological diagnose and the severity of the disease.

[figure not shown]

Figure 1: The overall study design. The numbers 1 to 6 indicate the sequence of Bulbicam measurements and *) the measurements using the Standard Method

4.2: Stratification

The two main strata are DR and AMD. The patients within each of these two strata will be divided in two sub-strata depending on the disease severity. Within each of the main strata, a third stratum will consist of gender- and age-matched HCs to the patients included in the two other sub-strata.

The three sub-strata within DR will be:

1. Healthy gender- and age-matched controls
2. Mild retinopathy: Mild nonproliferative retinopathy
3. Moderate retinopathy: Moderate nonproliferative retinopathy

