The three sub-strata within AMD will be:

1. Healthy gender- and age-matched controls
2. Early AMD
3. Intermediate AMD

4.3: Identification of patients

All information in the database will be anonymized and the activation key is stored by the clinically responsible ophthalmologist. The patients will be given one study identification number of six digits. The Id-number is divided in two parts in which the first part consists of four digits based on; country; site; disease and degree of the disease. Within these four-digit groups, two digits running number will be created by the DB-system.

- Digit 1:*** Indicate the country [1=Norway; 2=India i.e.]
- Digit 2:*** Indicate hospital site [1 = Site 1/Ullevål; 2= Site 2/Helgeland i.e.]
- Digit 3:*** Disease [0= Control; 1=Gla; 2=Cat; 3=DR; 4=AMD; 5=MS, i.e.].
- Digit 4:*** Degree of disease [0= none; 1= Mild/Early; 2=Moderate/Intermediate; 3=Severe].
- Digit 5&6:*** Running number within group [01= Patient 1; 02=Patient 2 i.e.]

V: Evaluation

5.1: Main variables

[figure not shown]
5.1.1: BulbiCam investigation

The main variables will be the variables recorded at the six Bulbicam tests described in the table below:

Table 2: The main variables with unit of the six Bulbicam test included in the study

TEST	VARIABLE	UNIT	FORMAT
NeuroField64	Seen/unseen (0)	0= unseen target	xml.
	Saccadic Reaction Time	Ms - 4 digits, 0 decimals	xml.
	Angular deviation	degree - 3 digits, 0 decimals	xml.
Ptosis	MDR1	mm - 2 digits, 2 decimals	xml.
	MDR2	mm - 2 digits, 2 decimals	xml.
Dynamic Acuity	Visual acuity	LogMAR 1 digit, 2 decimals	xml.
Dynamic Contrast	Contrast sensitivity	ConRatio 1 digit, 2 decimals	xml.
Dark Adaptation	Fixed contrast	Hz 1 digit, 1 decimal	xml.
	Fixed frequency	ConRatio 1 digit, 2 decimals	xml.
Pupil	Diameter (mm)	mm - 1 digit, 2 decimals	xml.
	Peak velocity	mm/s - 1 digit, 2 decimals	xml.
	Latency	Ms - 3 digits, 0 decimals	xml.
	RAPDlog	1 digit, 2 decimals	xml.

For Pupil module, a typical continuous recording of the pupil size and parameters is shown below:

LogCon defined as $-\log_{10}(\text{contrast ratio})$, EG if the low brightness part of the stimulus is 2 nits, the high brightness part 255 nits, the LogCon would be $-\log_{10}(2/255) = 2, 1$.

5.1.2: Standard investigation

The supporting variables will be recorded by the Standard (ST) investigation for DR and AMD.

Table 3: The supporting variables with unit of the standard eye investigation

Test	No of instances	Variable	Unit	Unit description

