An adverse event is any untoward symptom or sign befalling a patient in a clinical trial regardless of its relationship to the study medications. All adverse events must be described in detail and their severity and putative relationship to the study medication noted.

Adverse events may be considered seriously (SAE). The definition of this is as follows:

- Death
- Life threatening
- Leads to or prolongs hospitalization
- Results in persistent of significant disability
- Congenital anomaly

All adverse events will be recorded on relevant forms and their attribution to study medication will be evaluated. The severity of the reactions will be recorded along with a brief description of the event.

SAEs will be reported to sponsor and to the local sponsor representative via e-mail as soon as possible, but in any case, within 24 hours of the PI's knowledge of the event. It is the responsibility of the Principal Investigator to notify the Ethics Committee. It is the responsibility of the sponsor to report any Suspected Unexpected Serious Adverse Reactions (SUSAR) to the Regulatory Authority.

In case of SAE or SUSAR occurs, this will be handled in accordance with the hospital routines.

5.3: Patient factors

The patient factors recorded in the study will be age in days from birth to the screening visit calculated in the database and gender. The disease degree and previous and ongoing treatments of the disease will be recorded. Additionally, concomitant disease and treatments will be recorded.

Age and gender will be used to recruit controls to the included patients. Concomitant diseases and medication together with history of disease will be used to demonstrate the health condition of the participants at the time of inclusion in the study. Additionally, quality of life of the participants will be recorded at screening. This will also be a part of the health

evaluation but also gives the possibility of comparing the patients with the age- and gender matched controls.

VI: Study procedure

6.1: Trial equipment and clinical procedure

In this study only Bulbicum (BCAM) version 1.7 will be used. Additionally, ST will be performed as the starting examination

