8.2. Study Database

The validated data management system InCRF will be used for collecting the CRF data. The system selected is compliant with GCP guidelines and subject to 21 CFR (Code of federal regulations) FDA part 11 requirements. The final database will be stored in the Statistical Analysis system (SAS ver. 9.4 or later).

8.3: Data handling

A data entry person at site will enter the e-CRF data in InCRF and the DM will perform the initial data validation. In case of missing data, logical errors or interpretation problems, a query will be generated directly in InCRF. Investigator can review the query status via either InCRF function of “Study reports” /” Query report” or patient’s e-Form dashboard. When all the needed participants have finalized the clinical part, and the investigator has electronically signed the e-CRFs, the DM will do the final verification checks and perform final database hard-lock when all errors are corrected.

Screening analysis for logical errors will be evenly performed on this database and errors will be corrected after new information is collected from the site. When all the detected errors are corrected, the main basic database will be locked. The database will be transformed to a labeled SAS database, which also will be locked up to prevent all possible changes or additions. In this copy, the responsible statistician can make derivations but no corrections of the data. If corrections are needed, the main basic study database has to be re-opened and corrected. The international procedure for such changes will be followed.

IX: Discontinuation

A patient may discontinue the study at any time if, in the view of the investigator, it is in the participant's best interests. Alternatively, the participant has the right to discontinue her/his consent and exit the study without prejudice concerning her/his future treatment or care.

If a participant does not show up to an agreed visit, the investigator should try to motivate her/him to continue. However, if the participant has decided not to continue, she/he should be asked to attend a control visit as described for the end of the study (CRF VI).

9.1: Discontinuation not related to the study question

A participant who discontinues the study for administrative reasons or reasons documented not related to the trial equipment classifies as "Drop out" and has to be replaced by a new participant. Such participants will not be included in the statistical analysis.

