Additions to *Chapter 4.3*. All information in the database will be anonymized and the activation key is stored by the clinically responsible ophthalmologist.

Addition to *Chapter 8.1*. The identity of the participants in the database will be anonymized. The activation key is stored and only to be used by the clinically responsible ophthalmologist. Each study participants are given a study identification number which will be stored in the database

14.7: Ethical consideration

The previous statement under *Chapter 10.1*, page 34:” *No results from previous studies with this new equipment indicate any negative effect on the participants and AE has so far never been reported*” has been removed and replaced by “Despite that BulbiCam not previously has been used in any clinical study, it is nothing that may indicate that BulbiCam causes any adverse events.

The following specification is made in *Chapter 10.1*. All information in the database will be anonymized and the activation key is stored by the clinically responsible ophthalmologist

XV: Appendix**15.1: Set of CRF's***15.1.1: CRF I; Inclusion and exclusion***Case Record Form I (A=DR)**
(Inclusion and Exclusion criteria)

Study Id: V1_OTH /DR; AMD – I/2022; *Participant Initials:* _____*Participant category.* DR patient ; AMD patient ; Healthy Control without any ophthalmological or neurological disease

Inclusion criteria

- | | | |
|---|-------------------------------|--|
| A | Diagnosed with DR |  Yes  No |
| B | At least age of 18 years |  Yes  No |
| C | Without any other eye disease |  Yes  No |
-

Exclusion criteria

- | | | |
|----|--|--|
| 1 | Other visual disturbances and blindness |  Yes  No |
| 2 | Posterior Chamber Artificial Ocular Lens (PCIOL) |  Yes  No |
| 3 | Physical or psychiatric disease disturbing the measuring procedure |  Yes  No |
| 4 | Not able to perform full eye movements |  Yes  No |
| 5 | Visual acuity is less than 1 logMAR in any eye |  Yes  No |
| 6 | Visible part of the eye is abnormal. Haemorrhages/deformed pupils |  Yes  No |

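### Controls are matched 1:1 on age and gender, but the ID scheme and the CRF pages shown do not record the match or the control's diagnosis stratum, and the ANOVA stated in 11.2 names neither matching factor

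*Protocol*

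**What the plan says.** **Design.** Section 1.6 of the protocol: "Within each of the four strata, healthy matched controls related to gender- and age (1:1) will be included". Section 4.2 adds that within DR and within AMD "a third stratum will consist of gender- and age-matched HCs". Section 11.3 counts at least 16 HC and 16 patients for each diagnosis.

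**How controls are found.** Section 3.3: "The included patient will be asked if he/she know any person with same gender and age". Hospital staff are the fallback. Section 5.3: "Age and gender will be used to recruit controls to the included patients". No age tolerance is given.

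**What identifies a control.** In section 4.3 the third ID digit is "Disease [0= Control; 1=Gla; 2=Cat; 3=DR; 4=AMD; 5=MS, i.e" and the fourth is 0 for no disease. Then: "Within these four-digit groups, two digits running number will be created by the DB-system". CRF II repeats this coding and adds date of birth, gender and date of inclusion.

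**What the forms hold.** CRF I has a DR and an AMD version. Both offer the same category box, "Healthy Control without any ophthalmological or neurological disease". CRF III is pre-printed for DR or for AMD and has no control version. None of the CRF pages shown has a field for the matched patient or for the control's diagnosis stratum.

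**Replacement.** Under 9.1 a drop-out "has to be replaced by a new participant". Nothing is said about that person's matched partner.

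**Analysis.** Section 11.2 names ANOVA for patient groups against HC and mentions no age, gender or pair term.

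**The concern.** The protocol commits to individual matching and to two separate control strata, but its identification system can express neither. Every control at a site gets the prefix 1100 (Ullevål) or 1200 (Helgeland), whichever diagnosis it was recruited for.

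Two things are at stake:

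- **The record.** A later analysis plan can choose any model, but it cannot supply a link that the forms did not collect.
- **Precision.** Matching on age and gender makes the two groups alike on those factors. An ANOVA that leaves them out still counts their variation as residual error. If outcomes depend on age, the interval is too wide and the test too cautious, so part of the effort spent on matching is wasted.

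**Working it through.** **1. Does the ID or a form carry the match?**

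| Source | Control matched to DR | Control matched to AMD |
|---|---|---|
| ID digits 3 and 4 (4.3, CRF II) | 0, 0 | 0, 0 |
| ID digits 5 and 6 | running number in the shared group | running number in the shared group |
| CRF I category | Healthy Control box | same box |
| CRF III | no control version | no control version |
| Field for the matched patient | none shown | none shown |

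The CRF I version might hint at the stratum, but no rule says which version a control completes. The first inclusion item on each version is a diagnosis that no control can have.

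**2. The plan's own figure.** Inputs from 11.3: alpha 5%, power 90%, difference 1 SD, 16 per group. Sidedness is not stated. For independent groups n = 2(z_α + z_β)² per group.
- Two-sided: 2(1.960 + 1.282)² = 21.01, so 22 per group. With 16 v 16 the t-test has 78% power.
- One-sided: 18 per group, and 16 per group gives 88% by the normal formula.
- Two-sided, 16 patients against all 32 HC: 90.4% by the normal formula.

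The basis of the 16 is a separate matter. Below, 16 v 16 two-sided is the reference.

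**3. What leaving out the matching factors costs.** Let ρ be the within-pair correlation. It is not in the protocol, so it is assumed, with the range shown. The outcome SD is 1.
- True SE of the mean difference: √(2(1−ρ)/16). The unadjusted ANOVA uses about √(2/16) = 0.354 whatever ρ is.
- If ρ comes from age, adjustment for age and gender brings the residual variance to about 1−ρ on 28 degrees of freedom. At ρ = 0.3 the SE is √(1.4/16) = 0.296, the noncentrality 1/0.296 = 3.38 and the power 90%.
- The paired test has the same noncentrality on 15 degrees of freedom: 88%.
- Approximate type I error of the unadjusted test at ρ = 0.3: P(|Z| > 1.96/√0.7) = P(|Z| > 2.34) = 1.9%.

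Simulation agrees (100,000 trials per setting; 16 pairs; assumed age SD 10 years, control age within 2 years, linear age effect):

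| ρ (from age) | 0 | 0.2 | 0.3 | 0.5 |
|---|---|---|---|---|
| Power, unadjusted | 78.2% | 80.5% | 82.1% | 85.3% |
| Power, age + gender adjusted | 78.0% | 86.2% | 90.6% | 97.1% |
| Power, paired | 75.2% | 83.9% | 88.6% | 96.1% |
| Type I error, unadjusted (2 or 5 years) | 5.0–5.1% | 2.9–3.1% | 2.1% | 0.8% |
| 95% CI half-width in SD, unadjusted | 0.72 | 0.72 | 0.72 | 0.72 |
| 95% CI half-width in SD, adjusted | 0.72 | 0.64 | 0.60 | 0.51 |

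Adjusted and paired type I errors stay at about 5%. Widening the age tolerance to 5 years changes power by less than one percentage point.

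**4. If the correlation comes from other shared traits.** Acquaintances may be alike in ways other than age and gender. Adjustment then gains almost nothing, and only the pair link helps. At ρ = 0.3 power is 82.0% unadjusted, 82.5% adjusted and 88.6% paired.

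**The case against.** **Section 11.2 is silent; it does not exclude the matching.** ANOVA can carry covariates or blocks, and such detail is commonly left to an analysis plan, which is not shown here. This stands. A reader might infer that the protocol rules out a matched or adjusted analysis. It does not, and the cost above applies only if the ANOVA is run as literally stated.

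**The preferred analysis does not need the pair link.** Age and gender are already in CRF II. When the correlation comes from age, adjustment does at least as well as pairing at every ρ shown. This also stands. The link serves to document the strata of 4.2 and to allow a pair-blocked check.

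**The pairs may not be lost.** Patients name their controls, the investigator contacts them (3.3), and the investigator keeps a list of names and study numbers (10.4). CRF II gives site, gender, date of birth and inclusion date. A reader might infer that the link is irrecoverable. The documents do not support that: partial rebuilding is plausible. But the list is not said to record pairs, no age tolerance is stated, and replacements blur the picture. The form set in the text is also incomplete (CRF V and Figure 1 are not shown), so the statement is limited to the pages shown.

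**Comparing each diagnosis only with its own controls may be inferior.** Under a common linear age effect, all 32 HC with age and gender adjustment gave power of 88/93/96/99% at ρ 0/0.2/0.3/0.5, with type I error about 5%. This stands as a trade-off, so own-controls-only is not asked for here.

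**The four aims do not include a patient-against-HC comparison.** They are repeatability and stability, agreement with the Standard Method, and the normal ranges for patients and for a normal population. That limits the stakes, although 11.3 sizes the study on that comparison.

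**Conclusion.** The concern holds in limited form. The control strata and the 1:1 match planned in 1.6 and 4.2 are not documented by the ID scheme or by any CRF page shown, and the ANOVA in 11.2 is stated without the matching factors.

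Run as stated against own controls, the comparison is unbiased and errs on the cautious side. A reader might infer bias or a raised false-positive rate, but positive within-pair correlation lowers the type I error. The loss is one of precision: about 8 points of power and a half-width of 0.72 SD instead of 0.60 SD at ρ = 0.3, about 12 points at ρ = 0.5, and none at ρ = 0.

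These sizes rest on assumed ρ, age spread, age tolerance and a linear age effect. The protocol supports no particular value of ρ, so the direction is firm and the size is not. The change is worth making because it is cheap and because the link is much easier to record at enrolment than to reconstruct later.

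**What to change.** 1. **Section 11.2:** state that the patient-against-HC ANOVA is adjusted for age and gender. Both are already collected in CRF II. Cost: 2 degrees of freedom, about 0.2 points of power at ρ = 0 (78.2% to 78.0%).
2. **CRF I or II:** add one mandatory matched-patient ID field for controls, updated when either member is replaced under 9.1. The control's diagnosis stratum then follows from the patient's ID, and a pair-blocked sensitivity analysis becomes possible. Cost: one e-CRF field. The pair-blocked model loses about 3 points at ρ = 0 (78% to 75%), which is why it is proposed only as a sensitivity analysis.

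Whether each diagnosis is compared with its own 16 controls or with all 32 HC under age and gender adjustment is for the sponsor to decide and is not part of this fix.
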